7.10.2 Secondary Objectives

The secondary endpoints will be analyzed as follows:

1. The capability of the acceleration time from the FlowMet-R device to predict a vascular intervention or amputation will occur within three and six months following initial visit will be determined using the AUC from an ROC curve where the endpoint is vascular intervention or amputation within 7 months, which is the end of the 6 month follow-up window. The 95% CI of the AUC will be derived using the method described in DeLong, et al (1998) [15].
2. The capability of the acceleration time from the FlowMet-R device to predict a $\geq 50\%$ stenosis determined using the AUC from an ROC curve where the endpoint is vascular intervention or amputation within 7 months, which is the end of the 6 month follow-up window. The 95% CI of the AUC will be derived using the method described in DeLong, et al (1998) [15].
3. The correlations between the acceleration time from the FlowMet-R device and peripheral artery stenosis, changes in ABI, and changes in TBI will be computed using Pearson correlations. The changes for ABI and TBI will be as follows: 0 to 3 months, 0 to 6 months, and 3 to 6 months.
4. The correlation between the acceleration time from the FlowMet-R device and changes in Rutherford Classification will be computed using the Spearman correlation. The changes for Rutherford Classification will be as follows: 0 to 3 months, 0 to 6 months, and 3 to 6 months.

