Subjects enrolled in the Healthy cohort will be assessed according to Event Schedule C at a single time point. Imaging outside standard of care will not be performed on the healthy subjects, and healthy cohort subjects with normal ABI and TBI values will be assumed not to have significant peripheral arterial stenosis.

A registry will be established to store measurements acquired from patients who are enrolled in this study and who undergo surgical (re)intervention to address PAD-related symptoms. The collection of data during intervention may occur at any time following the initial and up to the final visit (6 month follow-up). Collected information will include, at minimum, a digitized copy of the intraprocedural record log, all timestamped angiographic films collected during the procedure, and continuous FlowMet-R data collected from the digits of the treated limb. This portion of the study is exploratory and considered hypothesis-generating. Therefore, no objectives or endpoints are currently established for data collected in the registry. For any subject undergoing (re)intervention during the course of this study, the treating physician and all associated site personnel will be blinded to the FlowMet-R outputs during the course of the procedure to eliminate any bias or procedural-based determinations on any outputs not validated.

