9.3 Scheduled Follow-up Visit Windows

The target dates and windows for each visit are detailed in the table below. Should a subject miss a visit or the visit fall outside the pre-specified window, a study deviation must be reported and the original follow-up schedule maintained for subsequent visits.

Data analyses include follow-up visits regardless of whether the visit occurs within the window. Therefore, a late visit is preferred over a missed visit, but must be accompanied by a deviation report. Follow-up visit windows are listed in Table 3, and are based on days post-FlowMet-R assessment.

Table 3: Data collection and study procedure requirements at subject visits

Study Follow-up Visit	Window (Calculated days post-FlowMet-R Assessment)		
	Window Start	Target	Window End
Follow-up Visit 1	2 months	3 months	4 months
Follow-up Visit 2	5 months	6 months	7 months

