9.10 Subject Exit, Withdrawal or Discontinuation

The study exit form should be completed at the time a subject is exited from the study. A subject will be considered to have exited from the study for any of the following reasons.

- Subject completes follow-ups required by the investigational plan
- Subject dies

- Subject requests to be withdrawn
- Physician requests that patient be withdrawn to protect the welfare of the patient
- Subject is lost to follow-up

A subject may elect to withdraw from the study at any time. The subject should notify the investigator. The investigator and research staff should encourage all subjects to return for required follow-up visits. Every attempt must be made to ensure all subjects complete the follow-up schedule. For subjects who fail to appear for a scheduled study visit, the site must contact the subject in a timely manner to reschedule the visit and associated required evaluations within the subject's window, if possible.

10. Risks and Benefits

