4.1.2 Secondary Objectives

The secondary objectives seek to discover the relationship between FlowMet-R measurements and several additional metrics important in vascular medicine. First, the capability of FlowMet-R in the prognosis of requiring a vascular intervention or amputation within three and six months following initial visit will be determined. Additionally, the correlation between FlowMet-R measurements and peripheral artery stenosis will be investigated. Finally, the correlation between changes in ABI/TBI/Rutherford Classification and changes in FlowMet-R data between any two time points will be assessed.

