4.1.2.1 Secondary Endpoints

- Utilize FlowMet-R data to create a predictive model for the prognosis of vascular intervention within a three and six month timeframe from initial visit.
- Employ the predictive model of PAD severity to generate an ROC curve for diagnosis of significant stenosis (>50%) in the iliac, femoral, popliteal, peroneal, or tibial arteries.
- Conduct a correlation test between the predictive model of PAD severity and greatest percent stenosis in the iliac, femoral, popliteal, peroneal, or tibial arteries.
- Conduct a correlation test between changes in the predictive model of PAD severity and corresponding changes in ABI, TBI, and Rutherford Classification between any two study time points.

5. Investigation Plan

This study is a non-randomized, multi-center, longitudinal study of healthy subjects and subjects with PAD who are scheduled for ABI, TBI, and either Duplex ultrasound or Angiographic assessments in a vascular clinic. Subjects will first be evaluated for study inclusion/exclusion. If the subject meets the inclusion criteria and wishes to enroll in the study, they will be asked to sign an informed consent form (ICF) and considered for enrollment. If the subject meets inclusion criteria and is enrolled, the subject will undergo approximately 3 minutes of FlowMet-R blood flow measurements in addition to their routine standard of care examination.

Subjects enrolled in the PAD cohort will be assessed according to Event Schedule A in the clinical investigation protocol (CIP) at approximately 0, 3 months, and 6 months. Subject follow ups must meet the scheduled time window within +/- 30 days. Subjects that require a vascular (re)intervention for PAD-related treatment before the final measurement (6 month follow up) will have pertinent data collected and saved in the study registry. The vascular procedure may change the timing with respect to the amount of months after baseline that the follow up visits occur. In that case, the standard of care follow up visits post intervention will be adhered to, and data will be collected from the follow up visits that correspond most closely to timepoints at 3 and/or 6 months post baseline visit.

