7.4 Handling of Missing, Unused, and Spurious Data and Dropouts

Data that is missing or incomplete will not be imputed. Complete case data will be used where all data for the respective analysis is available for a patient or visit.

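### SAP 7.10.2 item 1 asks a 3-month and a 6-month prognosis question but specifies one 7-month ROC: the 3-month question gets no analysis, and the 6-month one gets a proxy with uneven follow-up.

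*SAP*

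**What the plan says.** The SAP states the objective in Section 4.1.2 as "prognosis of requiring a vascular intervention or amputation within three and six months following initial visit will be determined". The matching endpoint in SAP 4.1.2.1 is a model for the "prognosis of vascular intervention within a three and six month timeframe from initial visit"; it keeps both horizons but does not mention amputation. Protocol 4.1.2 and 4.1.2.1 say the same. Protocol 12.1.2 uses intervention within 6 months as its example of a prognostic outcome.

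SAP 7.10.2 item 1 names the three- and six-month horizons and then sets one ROC analysis, "where the endpoint is vascular intervention or amputation within 7 months, which is the end of the 6 month follow-up window".

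Follow-up is set out as follows:

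- Protocol 9.3 gives the last visit as "Follow-up Visit 2 5 months 6 months 7 months" (window start, target, end). SAP Section 5 says "Subject follow ups must meet the scheduled time window within +/- 30 days".
- Protocol 9.10 lists among the reasons for exit "Subject completes follow-ups required by the investigational plan". Protocol Section 5 has intervention data collected up to the final visit.
- SAP 5.1 gives a minimum participation of 6 months for subjects with suspected PAD and 0 months for healthy subjects.
- SAP 7.1.3 puts every participant in the one analysis set, which serves every analysis. Anyone missing data for an analysis is left out of it.
- SAP 7.4 adds "Complete case data will be used where all data for the respective analysis is available for a patient or visit".

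SAP 7.12 records one change to the planned analysis, the reclassification of patients regardless of enrolment cohort.

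**The concern.** The objective contains two questions and the analysis section specifies one curve, at a horizon that is neither of them. A statistician following the SAP to the letter would have nothing to report for three months. The result offered for six months would be for a longer period, over which subjects are observed unequally.

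The outcome also lacks a working definition. The SAP does not say what makes a limb event-free when its last visit came before month 7, or how a death or a loss to follow-up is coded. Nor does it say whether a healthy limb, seen once, counts as a non-event. Two programmers could follow the text and obtain different AUCs. Healthy limbs matter most here: if they are counted as event-free without any follow-up, the curve partly measures how well the device separates healthy from diseased limbs, which is the primary objective and not a prognosis.

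**Working it through.** **1. Where the 7 months comes from.** Six months plus the 30-day tolerance, with a month of 365.25/12 = 30.44 days, is 6 + 30/30.44 = 6.99 months. Protocol 9.3 gives 7 months as the end of the window. The SAP's figure reproduces.

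**2. Horizons asked for and horizons analysed.**

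| Source | Horizon |
|---|---|
| SAP 4.1.2, objective | 3 and 6 months |
| SAP 4.1.2.1, endpoint | 3 and 6 months |
| Protocol 12.1.2, example | 6 months |
| SAP 7.10.2 item 1, opening | 3 and 6 months |
| SAP 7.10.2 item 1, ROC endpoint | 7 months only |

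Two ROC endpoints are required and one is supplied. It matches neither horizon, and SAP 7.12 does not declare the difference.

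**3. Time observed before 7 months, for a completer.** Unobserved time = 7 − month of final visit.

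- Final visit at month 5: 7 − 5 = 2 months, 2/7 = 29% of the horizon.
- Final visit at month 6: 7 − 6 = 1 month, 1/7 = 14%.
- Final visit at month 7 or later: none.

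The first line depends on which statement governs. SAP 5.1 promises at least 6 months of participation, while the visit window opens at month 5; the two need reconciling. If the 6-month minimum holds, a completer's gap is at most 1 month. Early exits can leave a larger gap than any of these.

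**4. Whether a 3-month analysis is feasible.** Anyone with an in-window final visit has been followed to at least month 5, which is past month 3. No extra visit is needed.

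**5. How close 7 months is to 6.** The documents give no event rate, so this is an illustration only. Assume a constant hazard and a 6-month risk R6 of 20% to 40%. Then R7 = 1 − (1 − R6)^(7/6).

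- R6 = 0.20: R7 = 0.229, and the share of 7-month events after month 6 is (0.229 − 0.200)/0.229 = 13%.
- R6 = 0.40: R7 = 0.449, and the share is (0.449 − 0.400)/0.449 = 11%.

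Varying the assumed 7-month risk from 10% to 50% moves the share only between 14% and 10%.

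**The case against.** The best defence is that the SAP explains its own figure. It calls 7 months the close of the 6-month window, so the natural meaning is any event up to and including the 6-month visit, with those who completed that visit counted as observed. On this reading 7 months is a practical stand-in for 6, and step 5 suggests that it is a close one. This stands, and it limits the complaint about the 6-month question. It does nothing for the 3-month question.

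A reader might infer three stronger points that the documents do not support.

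- *That the complete-case rule drops event-free completers and keeps those with events.* This requires ignoring the SAP's gloss on 7 months. Neither SAP 7.1.3 nor SAP 7.4 treats a subject who attended the 6-month visit as incomplete.
- *That the analysed outcome has about twice as many events as the 3-month one.* Under the assumptions of step 5, R3 = 1 − (1 − R6)^(3/6) = 10.6% to 22.5%, against 22.9% to 44.9% at 7 months. But both the constant hazard and the event rate are assumed. The Synopsis admits patients with an intervention already planned, so events may cluster early and the ratio would be smaller. In any case a ratio of event counts is not a bias in the AUC.
- *That up to 2 months per subject is a bound on unobserved time.* It conflicts with the 6-month minimum in one direction and with early exits in the other.

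Exit at the final visit is also partly inferred. Protocol Table 2 gives study exit its own column, and the event-schedule figures are not shown. No later contact is described in the text that can be read.

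Finally, SAP 7.2 presents the objectives as descriptive. That lowers the stakes, but a descriptive result still has to answer the question it is attached to.

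**Conclusion.** The point holds on the text alone, without any assumed rate. The 3-month prognosis has no specified analysis. The 6-month prognosis is answered by a 7-month proxy, with completers last seen anywhere between month 5 and month 7 and no coding rule for event-free limbs, deaths, early exits or healthy limbs.

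At six months the mismatch is probably modest: about 11% to 13% of 7-month events would fall after month 6, if the hazard is constant and the 6-month risk lies between 20% and 40%. The effect on the AUC at either horizon cannot be stated, because the documents give no event rate. As this is a secondary, descriptive objective, it should be corrected before analysis but does not threaten the primary result.

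**What to change.** In SAP 7.10.2 item 1, replace the single endpoint with two ROC analyses: vascular intervention or amputation by 3 months, and by 6 months, each using event dates counted from the initial visit. Keep the 7-month ROC as a sensitivity analysis. For each horizon, state that:

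- a limb is event-free only if it was observed to that horizon, with a written tolerance for subjects who completed the 6-month visit slightly early;
- deaths and exits before the horizon are coded by a named rule;
- healthy-cohort limbs are excluded, as an exception to SAP 7.1.3.

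Align SAP 4.1.2.1 with the objective on whether amputation counts, and record the 7-month analysis and its reason in SAP 7.12. If many subjects leave before a horizon, a time-dependent AUC weighted for censoring is a useful optional sensitivity analysis; it is not needed to repair the plan.

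The cost is SAP wording and a second run of the same code, with no new visits. Confirm first that the case report form captures the dates of interventions and amputations, since the documents do not show it. The downside is fewer events at 3 months and hence a wider confidence interval there.

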Subjects enrolled in the Healthy cohort will be assessed according to Event Schedule C in the CIP at a single time point. Imaging outside standard of care will not be performed on the healthy subjects, and healthy cohort subjects with normal ABI and TBI values will be assumed not to have significant peripheral arterial stenosis.

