5.2 Rationale

The study will assess the FlowMet-R's ability to provide a simple and continuous method of assessing PAD severity. To achieve the objectives defined in Section 4.1, FlowMet-R measurements will be acquired from the limbs of enrolled patients and the relationship between the FlowMet-R data and positive diagnosis of PAD and CLI will be evaluated at multiple time points (initial measurement, 3 month follow up, and 6 month follow up). Resulting sensitivity, specificity, accuracy, and ROC curves will be generated to demonstrate diagnostic capability. Changes in FlowMet-R data for enrolled patients at each study time point will be compared to corresponding changes in ABI, TBI, or patient symptoms. Finally, the prognostic capability of FlowMet-R data will be assessed by calculating the sensitivity and specificity of predicting whether surgical (re)intervention will be necessary following initial assessment.

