7.12 Changes to Planned Analysis

Patients will be classified based on definitions in Section 4.1.1.1.1 no matter the cohort they were originally enrolled in for the study.

8. Validation Requirements

To ensure the quality of the statistical results and datasets created for the study, the following validation requirements will be implemented. Programs that contribute directly or indirectly to the results pertaining to the primary and secondary objectives including TLG (Tables, Listings, and Graphs) development will be validated at least at level II by a statistician or a statistical programmer. Level I validation consists of a statistician or statistical programmer reviewer who independently programs output and then compares the output with that generated by the original statistician or statistical programmer according to the current work instruction. Level II: The peer reviewer reviews the code; where appropriate, performs manual calculations or simple programming checks to verify the output. Level III validation may be used for any previously validated program where only minor/administrative changes were made (e.g., change the location of the data directory). For level III validation, the original statistician or statistical programmer performs a visual inspection of the code and output to confirm functionality according to the current work instruction. Any results that are used for external publication or reports should be validated at levels I.

9. References

1. Mosely, L.H. and F. Finseth, Cigarette smoking: impairment of digital blood flow and wound healing in the hand. *The Hand*, 1977(2): p. 97-101.
2. Stadelmann, W.K., A.G. Digenis, and G.R. Tobin, Impediments to wound healing. *The American journal of surgery*, 1998. 176(2): p. 39S-47S.
3. Cronberg, C., et al., Peripheral arterial disease. *Acta Radiologica*, 2003. 44(1): p. 59-66.
4. Ouriel, K., Peripheral arterial disease. *The lancet*, 2001. 358(9289): p. 1257-1264.
5. Falanga, V., Wound healing and its impairment in the diabetic foot. *The lancet*, 2005. 366(9498): p. 1736-1743.
6. Norgren, L., et al., Inter-society consensus for the management of peripheral arterial disease (TASC II). *European Journal of Vascular and Endovascular Surgery*, 2007. 33(1): p. S1-S75.

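### SAP 7.10.2 scores the stenosis ROC against intervention or amputation, and correlates acceleration time itself, at no named visit, with changes in ABI, TBI and Rutherford

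*SAP*

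**What the plan says.** **Stenosis ROC.** Among the secondary endpoints, SAP 4.1.2.1 undertakes to "generate an ROC curve for diagnosis of significant stenosis (>50%) in the iliac, femoral, popliteal, peroneal, or tibial arteries". Protocol 4.1.2.1 has the same endpoint, and protocol 12.1.3 describes classifying each limb by stenosis above 50% in order to build that curve. The operative text is SAP 7.10.2 item 2. It names a threshold of 50% or more and then continues: "stenosis determined using the AUC from an ROC curve where the endpoint is vascular intervention or amputation within 7 months".

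**Change correlations.** SAP 4.1.2.1 says: "Conduct a correlation test between changes in the predictive model of PAD severity and corresponding changes in ABI, TBI, and Rutherford Classification". SAP 5.2 agrees: "Changes in FlowMet-R data for enrolled patients at each study time point will be compared to corresponding changes in ABI, TBI, or patient symptoms". SAP 4.1.2 states the same objective. The operative text differs. Item 3 of 7.10.2 specifies "The correlations between the acceleration time from the FlowMet-R device and peripheral artery stenosis, changes in ABI, and changes in TBI" by Pearson. Item 4 reads: "The correlation between the acceleration time from the FlowMet-R device and changes in Rutherford Classification will be computed using the Spearman correlation". Both items list the intervals 0–3, 0–6 and 3–6 months, but only for ABI, TBI and Rutherford.

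**Declared changes.** SAP 7.12 lists one change: "Patients will be classified based on definitions in Section 4.1.1.1.1 no matter the cohort they were originally enrolled in for the study". It mentions neither the stenosis ROC nor the correlations.

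**The concern.** SAP 7.10.2 is the text that a programmer will follow. In item 2 the label and the outcome disagree, and the outcome is the part that gets coded. A promised secondary analysis would then be missing, and an intervention AUC could be reported under a stenosis label.

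Items 3 and 4 replace the intended question, whether FlowMet-R moves when the haemodynamics move, with whether the FlowMet-R value at some visit goes with a change in haemodynamics. SAP 7.8 holds acceleration time at 0, 3 and 6 months, so a visit has to be chosen and none is named. If these points are settled only after data are seen, the visit, the threshold and the stenosis definition all become post hoc choices.

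**Working it through.** The plan states no figure for these analyses, so there is none to reproduce. The check compares the texts, then illustrates the size on assumed values.

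**1. Stenosis ROC, side by side**

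| Source | Predictor | ROC outcome |
|---|---|---|
| SAP 7.10.2 item 1 | acceleration time | intervention or amputation within 7 months |
| SAP 7.10.2 item 2 | acceleration time | intervention or amputation within 7 months |
| SAP 4.1.2.1, protocol 4.1.2.1 | FlowMet-R model value | stenosis >50% |
| Protocol 12.1.3 | – | stenosis >50%, per limb |

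SAP 7.2 makes the model value the acceleration time, so the predictors agree. Items 1 and 2 also share the DeLong interval. Run on the same limbs and visit, item 2 returns item 1's AUC. On another set of limbs, such as imaged limbs only, it returns a different AUC, but still one for intervention or amputation. No other SAP section supplies the stenosis curve. The threshold also differs: ≥50% in 7.10.2, >50% elsewhere.

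**2. Level against change**

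Let X be acceleration time and Y be ABI or TBI, each at baseline (0) and follow-up (1). Assume equal variances across visits, same-visit correlation r, a common lagged correlation l, and between-visit correlations ρ for X and ρ_Y for Y.

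- Intended: d = corr(X1−X0, Y1−Y0) = (r−l) / √[(1−ρ)(1−ρ_Y)].
- As written, baseline X: corr(X0, Y1−Y0) = (l−r) / √[2(1−ρ_Y)] = −d·√[(1−ρ)/2].
- As written, follow-up X: corr(X1, Y1−Y0) = +d·√[(1−ρ)/2].

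| ρ (assumed) | √[(1−ρ)/2] | Size at \|d\| = 0.30 | 0.50 | 0.70 |
|---|---|---|---|---|
| 0.5 | 0.500 | 0.150 | 0.250 | 0.350 |
| 0.7 | 0.387 | 0.116 | 0.194 | 0.271 |
| 0.8 | 0.316 | 0.095 | 0.158 | 0.221 |

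For example, with d = −0.50 and ρ = 0.7 the result is +0.19 using baseline and −0.19 using follow-up. A simulation of that case with 400,000 draws gave +0.192, −0.196 and, for change against change, −0.501.

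**3. Unequal SDs**

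Hold d at −0.50, take r = −0.4, −0.5 or −0.6 and the same ρ (0.5, 0.7 or 0.8) for both measures, and let the follow-up/baseline SD ratio of each measure vary.

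- Ratios 0.8, 1, 1.25: baseline result −0.04 to +0.37; follow-up result −0.37 to +0.04.
- Ratios 0.5, 1, 2: sizes reach 0.59, above the intended 0.50.

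Neither attenuation nor the sign reversal is therefore assured. These figures concern the Pearson results only; they do not apply to item 4 (Spearman, Rutherford).

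**4. Supporting point: the stenosis definition**

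Protocol 12.1.3 offers two computations of percent stenosis and the SAP selects neither. Method (1), distal PSV over proximal PSV, is a ratio. Read as a percentage, 1.2 becomes 120% and 1.9 becomes 190%. The table used for method (2) puts ratios under 2:1 below 50%. The two methods therefore classify every ratio between 0.5 and 2 differently at the 50% cut. The table's top class is 50%–99%, so a complete occlusion has no class.

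**The case against.** The best reply is that these are recognisable slips in secondary, descriptive analyses. Item 2 looks like item 1's clause carried over, and a statistician reading SAP 4.1.2.1 and 5.2 could recover the intent of all three items. SAP 7.2 says that the objectives are not hypothesis-driven. This limits the consequence but does not remove the contradiction. The lower validation level that SAP section 8 allows is a code review with output checks, and code that follows item 2 faithfully could pass it.

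It can also be said that the silence of SAP 7.12 proves little. That stands. Section 7.12 also omits the move from the trained model of protocol 12.1.2 to acceleration time, so it is not a full list of changes. The point rests on the conflict between sections of the SAP.

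A reader might infer that item 2 must print item 1's AUC twice. The SAP does not fix the limbs or the visit, so this holds only if they are the same. A reader might also infer that items 3 and 4 always give a weaker correlation of unpredictable sign. That depends on SDs and correlations that the documents do not give, and the unequal-SD cases show exceptions. Finally, a reader might take item 3's stenosis correlation to be faulty as well. It is not: SAP 4.1.2.1 asks for level against level there, and Pearson is an acceptable choice.

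**Conclusion.** Items 2, 3 and 4 of SAP 7.10.2 are wrong as written and need correcting. Item 2 yields no stenosis AUC. Items 3 and 4 yield a quantity other than the stated endpoint and leave the visit open. The text comparison needs no assumptions. The factors 0.50, 0.39 and 0.32 are illustrations for ABI and TBI that rest on equal variances, equal lagged correlations and assumed between-visit correlations.

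A reader might infer that the device's diagnostic claim is in doubt. The documents do not support that: the primary AUC in SAP 7.10.1 uses the PAD and CLI definitions and none of these clauses. The stenosis-percentage point is of lower severity. It does harm only if method (1) is the one chosen or if occlusions are left unclassified.

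**What to change.** All changes can be made in the SAP.

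- **Item 2.** Make the outcome significant stenosis, defined as the greatest duplex or angiographic stenosis in the limb, paired with acceleration time from the visit matched to that imaging. Count unimaged healthy-cohort limbs as negative under the rule already in SAP section 5: "healthy cohort subjects with normal ABI and TBI values will be assumed not to have significant peripheral arterial stenosis". Because those negatives are assumed, also report the AUC in imaged limbs only. Unimaged healthy-cohort limbs with abnormal ABI or TBI have no stenosis status; exclude them under SAP 7.4 and report their number.
- **Threshold.** Use one threshold in SAP 4.1.2.1, SAP 7.10.2 and the definition taken from protocol 12.1.3. Keeping >50% leaves the protocol text untouched; the SAP should then say that the table's 50%–99% class counts as significant.
- **Items 3 and 4.** For ABI, TBI and Rutherford, replace acceleration time with change in acceleration time over the same interval (0–3, 0–6, 3–6 months). Keep acceleration time against stenosis as a level, with Pearson.
- **Stenosis rule.** State that the >50% classification does not use method (1) and that complete occlusion counts as significant stenosis.

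The cost is SAP wording and minor programming. The inputs are already collected: acceleration time by visit and limb (SAP 7.8), ABI, TBI and Rutherford at baseline, 3 and 6 months (protocol 9.2), duplex velocities (9.7.4) and angiography (9.7.5). Editing protocol 12.1.3 itself would be an amendment needing IRB approval (protocol 14.6); setting the rule in the SAP avoids that.

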7.2 General Methodology

Data analysis will be performed by Medtronic employed statisticians/programmers. All statistical analyses will be generated using SAS version 9.4 or later or R version 4.1 or later software. Demographic and baseline characteristics will be summarized descriptively and will include age, gender, ethnicity, race, body mass index and hemodynamic measures (ABI, TBI, and acceleration time from the FlowMet-R device). For continuous variables, descriptive statistics will be presented including the number of

subjects with the measurement, mean, standard deviation, median, minimum and maximum. For categorical variables, descriptive statistics will include the number with the characteristic, the number evaluated, and the percentage.

Subject enrollment and accountability, visit attendance, and end of study status will be displayed using a STROBE like diagram and descriptive statistics, as appropriate. For each study visit, the following information will be tallied: completed visits, missed visits, deaths (if any), study withdrawals, and lost to follow-up. Compliance with study visits will be summarized as the percent of subjects available at each visit.

Missing data for endpoints may result from clinical assessments that were unable to be performed or data missing from the FlowMet device. These missing values will be excluded from summaries and analyses. In general, efforts will be made to minimize missing data and imputation of missing data will not be performed.

The objectives are not hypothesis-driven and therefore their results will be presented descriptively with no adjustments for multiple comparisons.

The value from the predictive model from the FlowMet-R measurements will be derived by the Research and Development team and will consist of the acceleration time.

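### SAP 7.10.2 correlates the level of acceleration time with changes in ABI, TBI and Rutherford class, although the endpoint is change against change; the result can have the wrong sign.

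*SAP*

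**What the plan says.** SAP 7.2 fixes what the FlowMet-R model value is: it "will be derived by the Research and Development team and will consist of the acceleration time". SAP 7.10.2 item 3 then gives the analysis: "The correlations between the acceleration time from the FlowMet-R device and peripheral artery stenosis, changes in ABI, and changes in TBI will be computed", as Pearson correlations. Item 4 reads: "The correlation between the acceleration time from the FlowMet-R device and changes in Rutherford Classification will be computed using the Spearman correlation". The intervals belong to the clinical measures: "The changes for ABI and TBI will be as follows: 0 to 3 months, 0 to 6 months, and 3 to 6 months", and item 4 lists the same three for Rutherford class. Neither item speaks of a change in acceleration time or says which visit's value to use.

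The endpoint these items are meant to analyse is different. SAP 4.1.2.1 says: "Conduct a correlation test between changes in the predictive model of PAD severity and corresponding changes in ABI, TBI, and Rutherford Classification". The objective in SAP 4.1.2 is that "the correlation between changes in ABI/TBI/Rutherford Classification and changes in FlowMet-R data between any two time points will be assessed". SAP 5.2 adds: "Changes in FlowMet-R data for enrolled patients at each study time point will be compared to corresponding changes in ABI, TBI, or patient symptoms". Protocol 4.1.2.1 carries the same endpoint. SAP 7.12 declares one change to the planned analysis, the classification of patients regardless of enrolment cohort. It does not mention this departure.

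**The concern.** Change against change asks whether the device moves when the limb's haemodynamics or symptoms move. Level against change asks whether limbs with long or short acceleration times are the ones whose ABI shifts. Regression to the mean alone produces a correlation of the second kind: a limb that is severe at the start of an interval tends to be less so at the end. Treatment between visits, which protocol section 5 allows for, could push the same way, but the documents give no data on that.

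Each interval also has two acceleration times, one at its start and one at its end, and the SAP does not choose between them. The reported direction could therefore depend on an unrecorded programming decision. A device that does follow change could be reported as unrelated, or inversely related, to ABI and TBI.

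**Working it through.** The documents give no expected correlation, power or sample size for these analyses, so there is no figure to reproduce. The text comparison above establishes the mismatch. The calculations below show what it can do. All correlations, reliabilities and spreads are assumptions. Longer acceleration time is taken to mean worse disease; if it runs the other way, every sign flips together and the contrast remains.

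**Model 1: stationary, no separate visit noise.** Acceleration time (AT) and ABI have unit variance, same-visit correlation -0.6, and a common autocorrelation *a* between visits.
- Variance of each change: 2(1 - a).
- Change against change: -0.6 × 2(1 - a) / [2(1 - a)] = -0.60 for any *a*.
- Start-of-interval AT against change in ABI: covariance -0.6a + 0.6 = 0.6(1 - a), so r = 0.6(1 - a)/√[2(1 - a)] = +0.6√[(1 - a)/2].
- End-of-interval AT: the same size with a minus sign.

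| a | change vs change | start level vs change | end level vs change |
|---|---|---|---|
| 0.4 | -0.60 | +0.33 | -0.33 |
| 0.6 | -0.60 | +0.27 | -0.27 |
| 0.8 | -0.60 | +0.19 | -0.19 |

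The end level keeps the sign but shows about 55%, 45% or 32% of the size (√[(1 - a)/2]).

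**Model 2: independent measurement noise at each visit.** AT = S + e and ABI = -S + u, where S is severity. Total variance is 1, *rel* is the share due to S, and *φ* is the autocorrelation of S.
- Change against change: -rel(1 - φ)/(1 - rel·φ).
- Start level: +rel(1 - φ)/√[2(1 - rel·φ)]. End level: the same size, negative.
- At rel = φ = 0.7: -0.21/0.51 = -0.41; start level 0.21/√1.02 = +0.21; end level -0.21.
- Over rel 0.5 to 0.9 and φ 0.3 to 0.9: change against change runs from -0.09 to -0.86, and start level from +0.05 to +0.52, always with the opposite sign.

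**Simulation of Model 2.** With 240 limbs (the PAD target in SAP 5.3), rel = φ = 0.7, limbs independent and 5,000 runs, the start-level correlation was significantly positive (r > 1.96/√237 = 0.127) in about 90% of runs. Mean change against change was -0.41. Attrition and paired limbs would lower that 90%.

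**Model 3: spread of severity differs between visits.** Baseline SD of S is 1, and noise variance is 0.43 on each measure.

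| follow-up SD | φ | change vs change | start level | end level |
|---|---|---|---|---|
| 0.5 | 0.5 | -0.47 | +0.49 | 0.00 |
| 0.5 | 0.8 | -0.34 | +0.44 | +0.16 |
| 1.3 | 0.8 | -0.42 | -0.03 | -0.37 |
| 1.6 | 0.8 | -0.54 | -0.17 | -0.54 |

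So a level can give a reversed result, a null one, or one of the right sign, depending on the visit chosen and on how spread changes.

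The Rutherford correlation (Spearman) was not simulated. The same mismatch applies to it, but no size is claimed.

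**The case against.** The strongest reply is that items 3 and 4 are shorthand. SAP 7.10.2 is introduced as the analysis of the endpoints, and the endpoint says changes on both sides. Acceleration time is merged by visit and limb (SAP 7.8), so its change can be computed, and a sensible programmer might do so. That reading is possible but weak. In item 3 the same phrase also serves the stenosis correlation, where it has to mean the level. The items write changes before ABI, TBI and Rutherford class and not before acceleration time. Even if change was intended, programming and validation will follow 7.10.2, so the text needs correcting.

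The second reply is that the numbers come from assumptions. This stands in part. The constant -0.60 follows from giving both measures the same autocorrelation and no visit-specific noise; with noise the benchmark shrinks. Reversal under stationarity needs the start-of-interval value, and growing spread can remove it. The idea that the worst limbs improve most through treatment is neither documented nor modelled. None of this makes a level a substitute for a change.

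Third, the endpoint is secondary and SAP 7.2 presents results descriptively. That limits the severity. It does not remove the problem: SAP 7.5 applies a 0.05 level and 95% confidence intervals to all analyses, and a wrong-signed estimate misleads without any test.

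**Conclusion.** The concern holds. Followed as written, the SAP contains no analysis that answers its last secondary objective, and the departure from the endpoint is not declared. The correlation it does specify can have the opposite sign to the change-against-change correlation: +0.19 to +0.33 against -0.60 in the noise-free stationary example, and +0.21 against -0.41 with measurement noise at reliability and autocorrelation 0.7. It can also be near zero, or keep the right sign at reduced size. Which of these occurs depends on the unnamed visit and on quantities the documents do not give, so the sizes are illustrative. The stenosis correlation in item 3 is not affected, because its endpoint concerns the level. This should be corrected before analysis. It touches a secondary, descriptive endpoint and leaves the primary AUC analysis unchanged.

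**What to change.** Rewrite the two items along these lines:

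- Item 3: Pearson correlation of the change in acceleration time with the change in ABI, and separately in TBI, for the same limb over the same interval (0 to 3, 0 to 6, 3 to 6 months).
- Item 4: Spearman correlation of the change in acceleration time with the change in Rutherford class, for the same limb and the same three intervals.

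State the expected sign of each. Give the stenosis correlation its own sentence, keep acceleration time there as a level, and name the visit it is paired with; that last detail is a clarification and not part of the defect. If the sponsor does want level against change, SAP 7.12 should say so, name the visit, and explain how the change-against-change endpoint will be met.

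The cost is two SAP sentences. Protocol 9.2 already schedules FlowMet-R, ABI/TBI and Rutherford assessments at baseline, 3 and 6 months, and SAP 7.8 already merges acceleration time by subject, visit and limb, so no new data are needed.
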